2. BACKGROUND

2.1 Copanlisib (BAY 80-6946)

A large rectangular area of the document is completely redacted with a solid black fill, obscuring the text underneath.A wide, horizontal rectangular area of the document is completely redacted with a solid black fill, obscuring the text underneath.A wide, horizontal rectangular area of the document is completely redacted with a solid black fill, obscuring the text underneath.A large rectangular area of the document is completely redacted with a solid black fill, obscuring the text underneath.

Copanlisib has been tested in approximately 772 patients with advanced cancers in either single-agent or combination studies. When given as a single agent, the most common drug-related adverse events (>20% of patients) included hyperglycemia, nausea, and hypertension. Other toxicities occurring with copanlisib administration included serious infections (19%), grade 4 neutropenia (12%), non-infectious pneumonitis (5%), and transient serious hypertension (1%) or hyperglycemia (1%).

For additional preclinical and clinical trial information, refer to the Investigator's Brochure.

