	Persistent glucose >500 mg/dL ¹	Withhold until pre-infusion glucose is <160 mg/dL (fasting)	Decrease by one dose level if repeated after 2 infusions. Discontinue if persistent at lowest dose level after at least one cycle, despite optimal tx and consult with diabetes specialist.		
	Max glucose >200mg/dL on subsequent days after infusion	N/A	N/A		
 Treatment with glucose-lowering medication per local standards Recommended (preferred order): SGLT2 inhibitor, DPP4 inhibitor, metformin, and/or thiazolidinedione Not recommended: Use of sulphonylurea/ metaglinides, insulin secretagogues to manage increased glucose levels post drug infusions

Drug-related AEs	Grade (CTCAE v5.0) or measurement	Action taken to study drugs	Retreatment Dose Level	AE management	Monitor and follow-up
Arterial Hypertension	Pre-dose BP >150/90 mmHg	Withhold ²	No change in dose	
 Consider BP-lowering medication 	
 Measure BP every 5-10 minutes (no more than 4 measurements) until acceptable for treatment.
	BP during infusion >160/100 mmHg	Interrupt if having symptoms attributable to hypertension ²	Next dose reduced by one dose level at PI's discretion	
 Initiate BP lowering medication according to standard of care 	
 Monitor BP as clinically indicated until <150/90.
	Post-dose BP >160/100 mmHg ³	N/A			
 Monitor BP as clinically indicated.
	Grade 4	Permanently discontinue	N/A		
Non-infectious Pneumonitis	Grade 2	Withhold	Decrease by one dose level		
	Grade 3 or 4 or recurrent Grade 2	Permanently discontinue	N/A		
Infections	Grade 3 or higher	Withhold	N/A		
	Suspected PJP infection of any grade	Withhold. Resume once infection resolves	N/A	If confirmed PJP, treat infection until resolution	Treat with concomitant PJP prophylaxis after resolution/ restarting of copanlisib
Dermatologic / Cutaneous AEs	Grade 2 ³	Withhold	1 st : no dose change 2 nd -3 rd : decrease by one dose level 4 th : discontinue		
	Grade 3 ³	Withhold	1 st -2 nd : decrease by one dose level 3 rd : discontinue		
	Grade 4	Permanently discontinue	N/A		
Hematological toxicity ⁴	Grade 2 neutropenia or thrombocytopenia on day 1 of each cycle	Withhold	No change in dose		

Table 4 - Dose modification and toxicity management guidelines for AEs associated with copanlisib					

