Drug-related AEs	Grade (CTCAE v5.0) or measurement	Action taken to study drugs	Retreatment Dose Level	AE management	Monitor and follow-up
	Grade ≥ 3	Withhold	Decrease by one dose level at the PI's discretion	
 • Treatment with transfusion or growth factors allowed at PI's discretion 	
Other non-hematological toxicities	Grade 3	Withhold	1 st : no dose change 2 nd -3 rd : decrease by one dose level 4 th : discontinue		
	Grade 4 or any toxicity requiring delay for >21 days	Permanently discontinue	N/A		

 1. Persistent occurrence is defined as repeated post-infusion blood glucose measurements taken at different times during the cycle despite optimal glucose-lowering therapy in consultation with endocrinologist 2. Infusion may proceed/resume on scheduled day if BP recovers to <150/90 mmHg for 2 consecutive measurements and symptoms (if present) resolve. 3. Despite maximum supportive therapy 4. Thrombocytopenia, neutropenia, febrile neutropenia, anemia, INR or PTT with bleeding 
General instructions:
 
 • For situations where drug is withheld due to a copanlisib-related AE, treatment can be resumed after AE has been reduced to Grade 1 or 0 unless otherwise indicated. Treatment should be permanently discontinued if AE does not resolve within 12 weeks of last dose. • If patient is already on lowest dose level and meets criteria for further decrease, study drug will be discontinued permanently. • Dose re-escalation may be allowed at the PI's discretion after patient has fully recovered from the toxicity and in the absence of any other adverse events that require dose-reduction, with the exception of non-infectious pneumonitis. • Abbreviations: SGLT2 = Sodium/Glucose co-transporter 2; DPP4 = Dipeptidyl peptidase 4; PJP= pneumocystis jiroveci pneumonia 					

In order to standardize the management of AEs for all subjects, treatment management algorithms are included in **Appendix C**. Additional AE treatment management algorithms included in the nivolumab IB might be considered for individual cases.

Subjects who require a delay in study treatment should be re-evaluated weekly or more frequently if clinically indicated and resume dosing when re-treatment criteria are met.

Subjects may resume treatment with study drug when the nivolumab-related AE(s) resolve to grade ≤ 1 or baseline value, with the following exceptions:

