4.4.2 Toxicity-Related Treatment Discontinuation

In addition to the discontinuation criteria listed in **Table 4** above, permanent discontinuation of study treatment should be considered for any severe or life-threatening treatment-related AEs, including, but not limited to, any of the following (the IND Sponsor and BMS must be notified in the event of these AEs):

- Any grade 2 treatment-related uveitis, eye pain, or blurred vision that does not respond to topical therapy and does not improve to Grade 1 severity within 2 weeks of starting therapy OR requires systemic treatment
- Any grade 3 non-skin, drug-related AE lasting > 7 days, with the following exceptions:
 - Grade 3 treatment-related uveitis, pneumonitis, bronchospasm, diarrhea, colitis, myocarditis, neurologic toxicity, hypersensitivity reaction, or infusion reaction of any duration requires discontinuation
 - Grade 3 treatment-related endocrinopathies adequately controlled with only physiologic hormone replacement do not require discontinuation. Treatment should be discontinued for grade 3 adrenal insufficiency.
 - Grade 3 treatment-related laboratory abnormalities do not require treatment discontinuation except:
 - Grade 3 treatment-related thrombocytopenia > 7 days **or** that is associated with bleeding requires discontinuation

- Any treatment-related liver function test (LFT) abnormality that meets the following criteria require discontinuation:
 - Total bilirubin $> 5 \times \text{ULN}$
 - Concurrent AST or ALT $> 3 \times \text{ULN}$ **and** total bilirubin $> 2 \times \text{ULN}$
- Any grade 4 treatment-related AE or laboratory abnormality, except for the following events which do not require discontinuation:
 - Grade 4 amylase or lipase abnormalities that are not associated with symptoms or clinical manifestations, or radiographic signs of pancreatitis.
 - Isolated grade 4 electrolyte imbalances/abnormalities that are not associated with clinical sequelae and are corrected with supplementation/appropriate management within 72 hours of their onset.
 - Grade 4 lymphopenia and leukopenia.
 - Grade 4 treatment-related endocrinopathy adverse events, such as ACTH deficiency, hyper- or hypothyroidism, or glucose intolerance, which resolve or are adequately controlled with physiologic hormone replacement (corticosteroids, thyroid hormones) or glucose-controlling agents, respectively, may not require discontinuation after discussion with and approval from the IND Sponsor.

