4.5 Duration of Therapy and Criteria for Removal from Study Treatment

In the absence of treatment delays due to adverse event(s), treatment may continue indefinitely until one of the following criteria applies. The reason for study treatment removal and the date the patient was removed must be documented in the Case Report Form.

A participant must be discontinued from study treatment but continue to be monitored in the study follow-up for any of the following reasons:

- The participant or participant's legally acceptable representative requests to discontinue study treatment
- Confirmed radiographic disease progression outlined in **Section 9** and **Appendix E**
 - As immunotherapy has been shown to cause pseudo-progression, patients are eligible to remain on study after progression if they are clinically stable, if they desire and their treating physician agrees it is in the interest of the patient. If subsequent imaging confirms progression, the patient's date of progression will be the date of first progression
- Clinical progression or deterioration

- Progression or recurrence of any malignancy, or any occurrence of another malignancy that requires active treatment
- Unacceptable adverse experiences as described in **Section 4.4.2** Exceptions must be approved by the IND Sponsor.
- The participant has a medical condition or personal circumstance which, in the opinion of the investigator and/or sponsor, placed the participant at unnecessary risk from continued administration of study treatment.
- Investigator's decision to withdraw the subject
- The participant has a confirmed positive serum pregnancy test
- Noncompliance with study treatment or procedure requirements

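### Table 4 allows Grade 4 hematological toxicity to be held and retreated, while sections 4.4.2 and 4.5 point to removal from treatment, and no passage says which governs

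*Combined protocol and SAP*

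**What the plan says.** **Table 4 (section 4.4.1).** For hematological toxicity of Grade 3 or above, the action is to withhold. The retreatment-dose column reads "Decrease by one dose level at the PI's discretion", and the next column allows transfusion or growth factors. Note 4 defines the row's scope: "Thrombocytopenia, neutropenia, febrile neutropenia, anemia, INR or PTT with bleeding". Under the table's general instructions, when drug is withheld, "treatment can be resumed after AE has been reduced to Grade 1 or 0 unless otherwise indicated". Infections of "Grade 3 or higher" are also withheld, with the retreatment dose level marked not applicable. Neither row has its own Grade 4 step.

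**Section 4.4.2.** This section presents itself as supplementing the Table 4 criteria, and its lead-in asks that permanent discontinuation be considered. One listed item is: "Any grade 4 treatment-related AE or laboratory abnormality, except for the following events which do not require discontinuation". The only blood-count exception is "Grade 4 lymphopenia and leukopenia". A separate item states that treatment-related Grade 3 thrombocytopenia requires discontinuation if it lasts more than 7 days or is associated with bleeding.

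**Section 4.5.** Unacceptable adverse experiences as described in 4.4.2 are among the reasons for which study treatment has to be discontinued. It adds: "Exceptions must be approved by the IND Sponsor".

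**The concern.** Two investigators can each follow the protocol and treat the same event differently. One reads Table 4, holds treatment for a brief Grade 4 neutropenia, and resumes on recovery at the same or a lower dose. The other reads 4.4.2 with 4.5 and takes the patient off treatment unless the IND Sponsor agrees otherwise. Whichever they choose departs from the other passage.

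At stake are patient safety after a Grade 4 event and uniform conduct in a multi-center trial. It also becomes hard to say what counts as a protocol deviation. For Grade 4 neutropenia this is not a remote case, because section 2.1 gives a rate of 12% with copanlisib.

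**Working it through.** **1. The same event under each passage**

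| Event (treatment-related) | Table 4 | 4.4.2 | 4.5 |
|---|---|---|---|
| Grade 4 neutropenia, thrombocytopenia or anemia | Withhold; resume at Grade 0 or 1; dose decrease optional | Falls under the Grade 4 item; not excepted; lead-in says to consider discontinuation | Discontinuation mandatory unless the IND Sponsor approves an exception |
| Grade 3 thrombocytopenia over 7 days or with bleeding | Same row, same action | Discontinuation required | As above |
| Grade 4 infection | Withhold; retreatment level not applicable; resumption only through the general instruction | Falls under the Grade 4 item; not excepted | As above |

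For Grade 4 neutropenia there are three different strengths of rule: resume, consider stopping, and must stop unless excepted.

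**2. Does Table 4 handle Grade 4 elsewhere?** Yes. It gives permanent discontinuation for Grade 4 hypertension, Grade 4 skin events and Grade 4 other non-hematological toxicity. The last of these does not reach blood counts, because its row is labelled non-hematological. A reader can reasonably take the absence of such a step in the hematological row as intended.

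**3. Can a precedence rule be inferred?** Try each in turn.
- If 4.4.2 with 4.5 governs, Grade 4 events cannot follow the hematological row's hold-and-retreat path unless the Sponsor has approved an exception. The Grade 4 part of that row then has no independent effect.
- If Table 4 governs, the Grade 4 item in 4.4.2 does not reach neutropenia, thrombocytopenia or anemia, and the Grade 3 thrombocytopenia item has no effect.

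Neither reading gives both passages full effect, and the text does not choose between them.

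**4. How many patients?** The plan states no figure for this. Inputs are n = 21 per cohort (sections 1.5 and 11.1) and p = 0.12 for Grade 4 neutropenia (section 2.1), assumed to carry over to the combination. Expected count = n × p, and P(at least one) = 1 − (1 − p)^n.

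| Rate p | Expected per 21 | P(at least one in 21) |
|---|---|---|
| 3% | 21 × 0.03 = 0.63 | 1 − 0.97^21 = 0.473 |
| 6% | 21 × 0.06 = 1.26 | 1 − 0.94^21 = 0.727 |
| 12% | 21 × 0.12 = 2.52 | 1 − 0.88^21 = 0.932 |
| 18% | 21 × 0.18 = 3.78 | 1 − 0.82^21 = 0.985 |

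Across both cohorts at 12%: 42 × 0.12 = 5.04 expected, and 1 − 0.88^42 = 0.995.

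**5. Design figures.** The two-stage rule (stop at 0 of 12, success at 3 or more of 21) gives type I error 0.0804 and power 0.803 by exact binomial calculation. These match the stated 0.08 and 0.80. The toxicity rules do not enter this calculation.

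**The case against.** The strongest answer is that the sections are meant to be read together. Section 4.4.2 says it adds to Table 4, and Table 4's resumption instruction yields where something else is indicated. On that view Table 4 gives the general action and 4.4.2 the specific stopping events. This is a fair reading, and it works best for prolonged or bleeding Grade 3 thrombocytopenia, where a specific rule sits on top of a general row. It does not settle Grade 4 toxicity. The section said to override asks only that discontinuation be considered, no precedence is stated, and the reading empties the Grade 4 part of the hematological row.

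It might also be said that the leukopenia exception covers neutropenia, or that 4.4.2 concerns nivolumab only. But the protocol uses neutropenia as its own term, both in the DLT list and in Table 4. Section 4.4.2 speaks of treatment-related events without limiting them to nivolumab.

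Oversight is not absent. Section 4.4.2 requires that the IND Sponsor and BMS be notified of these events, and section 11.2 provides weekly team meetings and investigator calls at least monthly. That helps detect divergent handling but does not say which handling is correct.

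Some stronger readings are tempting, and the documents do not support them:
- **That the PI decides whether the patient continues.** The PI's discretion appears in the retreatment-dose column and concerns the dose decrease (and, in the next column, transfusion or growth factors), not continuation.
- **That all these toxicities are common.** Only Grade 4 neutropenia has a rate. The 19% in section 2.1 is for serious infections, not Grade 4 infections, and no thrombocytopenia rate is given.
- **That the infection row is an equally clear conflict.** It never mentions resuming. Resumption comes only from the general instruction, with its qualifier.
- **That ORR or DCR would shift.** Patients with at least one dose stay evaluable for response unless they withdraw consent before re-evaluation (section 9.1), and those who stop without progression may still be scanned every 8 weeks (section 8.2, note 18). At the design's 20% response rate, 2.52 affected patients correspond to 2.52 × 0.20 = 0.5 expected responders. Only those stopped before responding could be lost.

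**Conclusion.** The inconsistency is real and stands in current text. It is clearest for Grade 4 neutropenia, thrombocytopenia and anemia. It is present but more open to a specific-over-general reading for prolonged or bleeding Grade 3 thrombocytopenia, and it is less clear for Grade 4 infection. Section 4.4.2 is softer on its face than a mandatory rule. The mandatory force for Grade 4 events comes from 4.5, and even that allows Sponsor-approved exceptions.

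At a 12% rate about 2.5 of 21 patients per cohort would meet the conflict, with a 93% chance of at least one; at 3% to 6% the chance is 47% to 73%. This assumes independent patients and that the rate applies to the combination. Section 2.1 does not state the denominator for the 12%, and its 772 patients come from both single-agent and combination studies. The number affected through the other events cannot be estimated.

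The consequence is for patient safety and consistent conduct across sites. A reader might infer damage to the primary analysis, but no effect on ORR, type I error or power is shown.

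**What to change.** Reconcile the hematological and infection rows of Table 4 with sections 4.4.2 and 4.5:
- State one action for each of: Grade 4 neutropenia, Grade 4 thrombocytopenia, Grade 4 anemia, Grade 3 thrombocytopenia beyond 7 days or with bleeding, and Grade 4 infection.
- Make the strength of the 4.4.2 lead-in agree with 4.5.
- State which passage governs when they differ, and who approves continuation after such an event.

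The clinical team chooses the action; this point takes no position on it. The cost is a wording amendment to Table 4, 4.4.2 and 4.5, with no new procedures, patients or change to the statistical design.

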4.4.2 Toxicity-Related Treatment Discontinuation

In addition to the discontinuation criteria listed in **Table 4** above, permanent discontinuation of study treatment should be considered for any severe or life-threatening treatment-related AEs, including, but not limited to, any of the following (the IND Sponsor and BMS must be notified in the event of these AEs):

- Any grade 2 treatment-related uveitis, eye pain, or blurred vision that does not respond to topical therapy and does not improve to Grade 1 severity within 2 weeks of starting therapy OR requires systemic treatment
- Any grade 3 non-skin, drug-related AE lasting > 7 days, with the following exceptions:
 - Grade 3 treatment-related uveitis, pneumonitis, bronchospasm, diarrhea, colitis, myocarditis, neurologic toxicity, hypersensitivity reaction, or infusion reaction of any duration requires discontinuation
 - Grade 3 treatment-related endocrinopathies adequately controlled with only physiologic hormone replacement do not require discontinuation. Treatment should be discontinued for grade 3 adrenal insufficiency.
 - Grade 3 treatment-related laboratory abnormalities do not require treatment discontinuation except:
 - Grade 3 treatment-related thrombocytopenia > 7 days **or** that is associated with bleeding requires discontinuation

- Any treatment-related liver function test (LFT) abnormality that meets the following criteria require discontinuation:
 - Total bilirubin $> 5 \times \text{ULN}$
 - Concurrent AST or ALT $> 3 \times \text{ULN}$ **and** total bilirubin $> 2 \times \text{ULN}$
- Any grade 4 treatment-related AE or laboratory abnormality, except for the following events which do not require discontinuation:
 - Grade 4 amylase or lipase abnormalities that are not associated with symptoms or clinical manifestations, or radiographic signs of pancreatitis.
 - Isolated grade 4 electrolyte imbalances/abnormalities that are not associated with clinical sequelae and are corrected with supplementation/appropriate management within 72 hours of their onset.
 - Grade 4 lymphopenia and leukopenia.
 - Grade 4 treatment-related endocrinopathy adverse events, such as ACTH deficiency, hyper- or hypothyroidism, or glucose intolerance, which resolve or are adequately controlled with physiologic hormone replacement (corticosteroids, thyroid hormones) or glucose-controlling agents, respectively, may not require discontinuation after discussion with and approval from the IND Sponsor.

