4.3 Dose Limiting Toxicities

Dose limiting toxicities (DLTs) are defined as any AE occurring within the first cycle of treatment that is temporally related to study drug administration, which is not due to the subject's underlying malignancy, for which there is no clear evidence for an alternative etiology, and that meets one of the following NCI CTCAE criteria:

Hematologic Toxicities

- Grade 4 anemia
- Grade \geq 3 neutropenia lasting \geq 14 days
- Grade \geq 3 febrile neutropenia
- Grade 4 thrombocytopenia, or Grade 3 thrombocytopenia with clinically significant bleeding

Other Toxicities

- Treatment-related \geq grade 4 AEs, except transient hyperglycemia
- Grade \geq 3 Pneumonitis or recurrent Grade 2 pneumonitis
- Grade \geq 3 Nephritis
- Grade \geq 3 elevated AST, ALT
- Grade \geq 2 eye pain or reduction of visual acuity that does not respond to topical therapy and does not improve to \leq grade 1 severity within 2 weeks of starting therapy, or requires systemic therapy
- Any other Grade \geq 3 toxicities except
 - Grade 3 nausea, vomiting, or diarrhea that resolves to Grade \leq 1 within 7 days, with or without appropriate supportive therapy
 - Grade 3 rash that resolves to Grade \leq 2 within 7 days
 - Grade 3 fatigue that resolves to \leq Grade 2 within 14 days

- Grade 3 transient hypertension and transient hyperglycemia
- Grade ≥ 3 laboratory abnormalities that, in the judgment of the investigator, are not clinically significant
- Asymptomatic amylase/lipase elevation

Unexpected Grade 3 or greater laboratory abnormalities should be repeated within 24-72 hours if clinically indicated and monitored as necessary to determine if event meets toxicity criteria.

Table 3 – Dose De-Escalation Rules

Number of Patients with DLT at a Given Dose Level	Dose De-Escalation Decision Rule (dose levels found in Table 1)
0-1 out of 3	Enter 3 more patients at this dose level 
 • If ≤ 1 of 6 subjects in this cohort experience a DLT, this is the recommended phase II dose (RP2D) • If ≥ 2 of 6 patients in this cohort experience a DLT, this dose level exceeded the RP2D. 3 patients will be entered at the next lower dose level.
≥ 2 out of 3	This dose level exceeded the RP2D. 3 additional patients will be entered at the next lower dose level.

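### A Phase I patient actually stopped in Cycle 1 for brief Grade 3 diarrhoea is scored DLT-free when the RP2D is chosen

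*Combined protocol and SAP*

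**What the plan says.** **DLT definition (4.3).** Other Grade 3 or higher toxicities count as DLTs, with listed exceptions. One is "Grade 3 nausea, vomiting, or diarrhea that resolves to Grade" 1 or lower within 7 days. Another is "Grade 3 fatigue that resolves to" Grade 2 or lower within 14 days. The haematologic list names thrombocytopenia at Grade 4, or at Grade 3 with clinically significant bleeding. No criterion mentions stopping treatment.

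**Stopping for toxicity (4.4.2).** This section adds to the discontinuation rules in Table 4. Its lead-in is soft: "permanent discontinuation of study treatment should be considered for any severe or life-threatening treatment-related AEs". One listed item is "Any grade 3 non-skin, drug-related AE lasting > 7 days", and under it comes the firm statement "Grade 3 treatment-related uveitis, pneumonitis, bronchospasm, diarrhea, colitis, myocarditis, neurologic toxicity, hypersensitivity reaction, or infusion reaction of any duration requires discontinuation". The same section also requires discontinuation for treatment-related Grade 3 thrombocytopenia that either lasts more than 7 days or comes with bleeding.

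**Removal from treatment (4.5).** "A participant must be discontinued from study treatment but continue to be monitored in the study follow-up for any of the following reasons"; the reasons include the unacceptable adverse experiences described in 4.4.2, with the rider "Exceptions must be approved by the IND Sponsor".

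**Dose decision (Table 3 and 11.1).** Two or more DLTs in the first 3 patients end the level. Otherwise 6 are treated, and the level becomes the RP2D if at most 1 of 6 has a DLT. Section 4.2 evaluates every patient enrolled at a level for DLTs over the 28-day first cycle, and 9.1 makes everyone dosed evaluable for toxicity. The only replacement rule (9.1, 11.1) concerns withdrawal of consent before disease re-evaluation, and it serves the response endpoint.

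**The concern.** The RP2D is the Phase I primary objective, and it rests on a count in six patients. A toxicity can be severe enough to take a patient off both drugs for good and still leave no mark on that count. The patient stays in the denominator as a success for tolerability. If the stop follows the Day 1 dose, that patient has had one of three planned Cycle 1 copanlisib doses, or one of two on the every-two-weeks schedule (1.5).

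The mismatch works in one direction only: leaving these patients uncounted can turn a failing level into an accepted one, never the reverse. The accepted dose is then given to the 42 patients planned for Phase II.

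**Working it through.** **Step 1. Compare the rules event by event, for treatment-related events in Cycle 1.**

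| Event | DLT under 4.3? | Stop under 4.4.2 and 4.5? | Gap? |
|---|---|---|---|
| Grade 3 diarrhoea, Grade 1 or lower within 7 days | No, exempt | Required whatever the duration; sponsor may grant an exception | Yes |
| Grade 3 thrombocytopenia over 7 days, no bleeding | Not in the haematologic list; may fall under the general Grade 3 line | Required | Apparent; depends on how the general line is read |
| Grade 3 fatigue lasting 8 to 14 days, then Grade 2 or lower | No, exempt | To be considered, as a Grade 3 event beyond 7 days | Weak; discretionary |
| Other Grade 3 events named with diarrhoea in 4.4.2 (pneumonitis, colitis, myocarditis and so on) | Yes; none is exempt | Required | No |

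I do not claim that the table is exhaustive, which is one reason to word the fix generally.

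**Step 2. The effect on the decision, which needs no assumed rate.** Take six patients, one with a counted DLT and another stopped in Cycle 1 for brief Grade 3 diarrhoea. As written, the count is 1/6 and the level is accepted. With the stop counted, it is 2/6 and the level fails.

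**Step 3. Illustration.** The plan states no operating characteristic for Phase I, so there is no figure of its own to reproduce. Let *p* be the chance that a patient scores a DLT. Any path stopped at 2 or more of 3 also has at least 2 of 6, so the two-stage rule reduces to

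P(accept) = (1−p)^6 + 6p(1−p)^5.

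At p = 0.20: 0.2621 + 0.3932 = 0.6554.

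Let *d* be the true DLT rate under 4.3 as written and *q* the rate of uncounted Cycle 1 stops, taken to fall in different patients. Then p = d as written and p = d + q if the stops count. **Both d and q are assumptions; neither is in the documents.** Counting more events can only move a level from accept to fail, so the difference is the probability that the decision changes.

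| d | q | Accept, as written | Accept, stops counted | Decision changes |
|---|---|---|---|---|
| 10% | 1% | 0.8857 | 0.8655 | 0.0202 |
| 10% | 2% | 0.8857 | 0.8444 | 0.0414 |
| 10% | 5% | 0.8857 | 0.7765 | 0.1093 |
| 20% | 1% | 0.6554 | 0.6308 | 0.0246 |
| 20% | 2% | 0.6554 | 0.6063 | 0.0491 |
| 20% | 5% | 0.6554 | 0.5339 | 0.1214 |

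Differences were taken before rounding.

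**Step 4. Levels accepted on exactly one DLT.** Each of the other five patients has an uncounted stop with probability q/(1−d), so the chance that the level would fail if stops counted is 1 − (1 − q/(1−d))^5. At d = 20% this is 6.1%, 11.9% and 27.6% for q = 1%, 2% and 5%.

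**The case against.** The strongest reply is that the plan does not make stopping certain. The 4.4.2 lead-in asks only that discontinuation be considered. Table 4 handles a first Grade 3 event among other non-haematological toxicities by withholding and resuming at the same dose. Section 4.4.1 lets treatment resume once diarrhoea is back to baseline, with no grade limit stated. Section 4.5 allows sponsor exceptions. The gastrointestinal algorithm in Appendix C might settle the matter, but it is a figure I could not see.

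This stands in part. A reader might infer that every patient with brief Grade 3 diarrhoea is taken off treatment and therefore miscounted; the documents do not support that. They do make stopping the default: the diarrhoea item says it is required, 4.5 says must, and 4.4.2 applies on top of Table 4. The resumption rule still has work to do for Grade 2 diarrhoea, which 4.4.1 delays when nivolumab-related. And whichever reading is right, a patient who *is* stopped scores as DLT-free.

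A second reply is that the two rules have different purposes. The DLT rule sets the copanlisib dose, while 4.4.2 protects the individual. Nivolumab is never reduced, so de-escalation may not address an event it caused. That is a fair reason to exempt brief, reversible diarrhoea, and the exemption should stay. It is a weaker reason to score as tolerated a regimen that a patient had to leave for good.

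Third, sponsor notification, the weekly team meetings and the Phase II toxicity guideline in 11.4 make such events visible. They do, but they leave the 4.3 count unchanged.

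Finally, the event may be uncommon. It must be Grade 3, treatment-related, in Cycle 1, brief, in a patient without another DLT, and followed by an actual stop. The decision then changes only alongside a counted DLT or a second such patient. This stands, and it limits the weight of the point.

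**Conclusion.** The point holds for patients actually stopped. Diarrhoea is the clear case, thrombocytopenia a probable one subject to how 4.3 is read, and fatigue a minor one. The firm result is the change from 1/6 (accept) to 2/6 (fail) when one such stop accompanies one counted DLT.

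The size beyond that is unknown. Under assumed rates of 10% or 20% for DLTs and 1% to 5% for uncounted stops, the decision changes in about 2% to 12% of dose levels tested. These figures show sensitivity only; they are not estimates for this trial, and the upper end depends entirely on the assumed 5%.

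A reader might also infer that the RP2D carried into Phase II is too high. The documents report no Phase I outcomes, so nothing in them supports that. This is a gap in a rule, worth closing because closing it is cheap, and it does not show that the wrong dose was chosen.

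**What to change.** Add after the exceptions in 4.3:

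> *Any treatment-related AE in Cycle 1 that leads to permanent discontinuation of study treatment (under Table 4, Section 4.4.2 or Section 4.5) counts as a DLT, even if listed above as an exception.*

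Add to 4.5:

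> *For a Phase I patient in Cycle 1, any exception approved by the IND Sponsor is documented before the DLT count for that dose level is reviewed.*

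Leave the exemptions and the stopping rules as they are, so that brief diarrhoea after which treatment continues remains exempt.

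If Phase I is complete, report Cycle 1 permanent discontinuations for toxicity beside the DLT count at each dose level, and state whether at most 1/6 still holds with them counted.

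**Cost.** Two sentences, or one extra column in a table. No extra patients are needed at a level that still passes; a level that fails moves to the next lower one, within the existing maximum of 18.

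**Downside.** A brief event that ends treatment can contribute to de-escalation. For diarrhoea as well as fatigue, DLT status then depends partly on the decision to stop or to grant an exception. Documenting exceptions before the count is reviewed makes that discretion visible but does not remove it.
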